|  Other household member |  Guardian Institution or organisation |
|  Relative |  Other(specify) |

8b. If the phone is not the client's does the owner know of the client's status?

- Yes
 No
 Unknown

9. Secondary Telephone Contact:

--	--	--	--	--	--	--	--	--	--	--	--	--	--	--	--	--	--	--	--

- Mobile
 Landline
 Unknown

9a. Line belongs to:

- | | |
|---|---|
|  Client |  Friend |
|  Parent |  Neighbour |
|  Caregiver |  Nearby Simu ya Jamii |
|  Other household member |  Guardian Institution or organisation |
|  Relative | |
|  Other(specify) | |

9b. If the phone is not the client's does the owner know of the client's status?

- Yes
 No
 Unknown

10. How long has the client been living at this residence:

Years

 Months

10a. This residence is:

- Permanent
 Temporary
 Unknown

For the data use only (tick after scanning the form)

Scanned Date ___ / ___ / _____ Name of data person

HOPE CLINIC

ADULT MEDICAL FOLLOW-UP

HOPE ID Number

Site Code

Today's Date (DD.MM.YYYY)

/

/

Interviewer number

HISTORY OF PRESENT ILLNESS

MEDICAL REVIEW

1. Does the patient currently have Extra pulmonary TB? Yes No

2. Does the Patient have Pulmonary TB? Yes No *(If YES go to 2a, If NO go to 4)*

2a. If YES, what was the diagnosis based on (tick all that apply)

- Chest X-ray
- Sypmtoms (persistent cough >2 weeks, fever, night sweats, etc)
- Failure to respond to empirical antibiotics
- Sputum
- Other (specify)
- Unknown

3. Is the patient currently on treatment for TB(PTB & ETB) *(If YES go to 3a, If NO or Unknown go to 4)*
 Yes No Unknown

3a. If yes, specify treatment start date (DD.MM.YYYY) / /

3b. If YES, specify treatment

- EH SHRZE
- RHZ unknown
- RHZE Other (specify)
- RH

S=streptomycine
 H=Isoniazid
 R=Rifampicin
 Z=Pyrazinamid
 E=Ethambutol

3c. Is the patient currently being treated for TB at coptic? Yes No *(If YES go to 4, If NO go to 3d)*

3d. If NO, specify where:

- Private hospital
- Public hospital
- Other government facility
- Other (specify)

4. In the past month, has the patient experienced any of the following? (tick all that apply)

- Dysparenuia Testicular pain or swelling
- Genital sores or ulcers Urethral discharge
- Lower Abdominal pain Vaginal discharge
- Painful micturation(Dysuria) Vaginal itching/burning
- None

MEDICATIONS

5. Is the patient currently taking HAART or ARVs, excluding PMTCT & PEP? Yes No (If YES go to 5a, If NO go to 7)

5a. If yes, specify (tick one)

- | | |
|--|---|
|  AZT-3TC-EFV |  d4T(40mg)-DDI-LPV/rit |
|  AZT-3TC-NVP |  TDF 3TC EFV |
|  AZT-3TC-LPV/rit |  TDF 3TC NVP |
|  d4T(30mg)-3TC-EFV |  TDF-ABC-LPV/rit |
|  d4T(30mg)-3TC-NVP |  Unknown |
|  d4T(30mg)-DDI-LPV/rit |  Other (specify)  |

5b. Has the patient had any recent side effects due to HAART or ARV medications? Yes No (If Yes go to 5c, If NO go to 6)

5c. If YES, describe the symptoms and severity of possible side effects (Tick for each symptom)

Symptom	Frequency of Symptom	If YES, severity of symptom
a. Nausea or vomiting	 Sometimes  Often	 Mild  Moderate  Severe
b. Rash	 Sometimes  Often	 Mild  Moderate  Severe
c. Fat changes	 Sometimes  Often	 Mild  Moderate  Severe
d. Diarrhea	 Sometimes  Often	 Mild  Moderate  Severe
e. Anemia	 Sometimes  Often	 Mild  Moderate  Severe
f. Cough	 Sometimes  Often	 Mild  Moderate  Severe
g. Fatigue	 Sometimes  Often	 Mild  Moderate  Severe
h. Abdominal pain	 Sometimes  Often	 Mild  Moderate  Severe
i. CNS - dizziness, anxiety, nightmares	 Sometimes  Often	 Mild  Moderate  Severe
j. Headache	 Sometimes  Often	 Mild  Moderate  Severe
k. Jaundice	 Sometimes  Often	 Mild  Moderate  Severe
l. Difficulty breathing	 Sometimes  Often	 Mild  Moderate  Severe
m. Burning/numbness/tingling	 Sometimes  Often	 Mild  Moderate  Severe
n. Fever	 Sometimes  Often	 Mild  Moderate  Severe
o. Heartburn	 Sometimes  Often	 Mild  Moderate  Severe
p. Other (specify) 	 Sometimes  Often	 Mild  Moderate  Severe

6. During the last 7 days how many ARV pills did the patient MISS taking? (tick one)

- None Very Few Half Most All

6a. If patient MISSED doses, please specify reasons (tick all that apply).

- Alcohol Forgot Too ill
 Depression Inability to pay Toxicity/side effect
 Drug stock out - dispensary Patient lost or ran out of pills Other (specify)
 Delivery/travel problems Stigma, disclosure or privacy issues
 Felt better Share with others

7. Is patient taking any of the following medications? (tick all that apply)

- Cotrimoxazole Antimalarial medications None of the above
 Dapsone Herbal traditional medications
 Fluconazole Multivitamin supplements

8. What other medications is patient currently taking?

Medication	Dose (mg)	Frequency (per day)	Start date	Stop date
1.				
2.				
3.				

9. PHYSICAL EXAMINATION

Nurse number

Temp (F) HR BP / RR Wt (Kg) HGT Sa O2

BMI BMI > 18.5 BMI < 18.5 BMI Unknown Gender MALE Female

10. System (tick one)	Normal	Abnormal	Not done	Findings (if abnormal)
General				
Skin				
Lymph nodes				
HEENT				
Lungs				
Cardiovascular				
Abdomen				
Genitourinary				
Extremities				
Musculoskeletal				
Neurological				
Psychological				

ASSESSMENT AND PLAN

11. What diagnoses does the patient have on today's visit (tick all that apply)?

- | | | | |
|---|--|--|--|
|  Anaemia |  Dermatitis |  Myalgia |  URTI |
|  Asthma |  Extra Pulmonary TB |  Neuropathy |  UTI |
|  Candidiasis (thrush) - oral |  Gonorrhoea |  Peptic Ulcer disease |  Zoster |
|  Candidiasis (thrush) - vaginal |  Genital Ulcer disease |  Pneumonia |  None |
|  Chancroid |  Hypertension |  Side effects due to ARV |  Other (specify) |
|  Conjunctivitis |  HSV - genital |  Soft tissue infection |  |
|  Diarrhea |  IRIS |  Syphilis | |
|  Dementia |  Malaria |  Ulcers - oral | |

12. What is the patients current Pulmonary TB diagnosis?

- Pulmonary TB suspected *(If suspected go to 13)*
- Pulmonary TB diagnosed today *(If diagnosed go to 14)*
- Currently on pulmonary TB treatment *(If currently on TB treatment go to 15)*
- Previously diagnosed with TB, not on Treatment *(skip to 14a)*
- No Pulmonary TB *(If NO TB go to 15)*
- Other(specify)

13. If pulmonary TB suspected, what is the suspected pulmonary TB based on (tick all that apply)?

- Abnormal X-ray
- Symptoms (persistent cough >2 weeks, fever, night sweats, etc)
- Failure to respond to empirical antibiotics
- Recent contact with people with Pulmonary TB
- Other (specify)

13a. Will the patient be sent for pulmonary TB testing? Yes NO *(If yes, go to 13b, if no go to 15)*

13b. If YES, which of the following tests will the patient be sent for:

- Sent for sputum
- Sent for X-ray
- Other (specify)
- (Go to 15)*

14. If Pulmonary TB is diagnosed today, what is it based on (tick all that apply)?

- Abnormal X-ray Failure to respond to empirical antibiotics
- Symptoms (persistent cough >2 weeks, fever, night sweats, etc) Sputum
- Other (specify)

14a. Specify treatment to be started: S=streptomycine

- | | | |
|--|--------------------------------|---------------|
|  RHZE |  SHRZE | H=Isoniazid |
| | | R=Rifampicin |
|  RHZ |  EH | Z=Pyrazinamid |
| | | E=Ethambutol |
|  Other (specify) |  | |

Section B: Female Patients Only (If Male go to 19)

15. Is the patient currently pregnant?
 Yes No Unknown *(If YES, complete Pregnancy Monitoring Form)*
16. Is the patient currently breastfeeding? Yes No *(If YES, go to 16a, if no go to 17)*
 16a. If yes, specify what type of breastfeeding (tick one)
 Exclusive breastfeeding *(Child given ONLY mother's milk and NO water, tea, formula, cow's milk or food of any kind)*
 Mixed feeding *(Child given mother's milk and water, tea formula, cow's milk or food)*
- 16b. If YES, has she had a session with the nutritionist since she started breast feeding?
 Yes No ***(If NO, refer patient to Nutritionist)***
17. Has the patient delivered in the past 18 Months? Yes No *(If yes go to 17a, If No go to 18)*
 17a. If yes, is this the first time the patient has returned to the Hope Center since delivery?
 Yes ***(If yes, complete pregnancy Close -Out form)***
 No
- 17b. Age of the child Months Days Child not Alive
- 17c. If not currently breastfeeding, at what age did the child stop breastfeeding?
 Months Days Unknown NA, Child never breastfed
- 17d. Has the child ever had a PCR test? Yes No
- 17e. If Yes, what was the result of the last PCR test?
 HIV Positive *(Go to 18)*
 HIV Negative
 Indeterminate
 Result not yet available
(Complete Infant PCR form; If Q17e is HIV Negative, Indeterminate or Result not yet available)
- 17f. Will an Infant PCR test be ordered today? Yes No
18. Is the patient being referred for Cervical Cancer screening at Hope? Yes No *(If yes go to 19, If NO go to 18a)*
 18a. If NO, reasons why patient NOT referred for Cervical Cancer Screening *(tick all that apply)*
 Patient is younger than 18 years
 Patient has had total hysterectomy, LEEP or cryotherapy
 Patient is currently pregnant
 Patient has had a screening test in the last year
 No service available at this time
 Patient wishes to defer until a later time Specify reason
 Patient does not accept screening Specify reason
 Other(specify)

19. Is the Client currently on HAART, excluding PMTCT and PEP? Yes No *(If YES go to 19a, If No go to 19b)*

19a. If yes, did you continue current HAART? Yes No *(If YES go to 20, If No go to 19a1)*

19a1. If no, did you change or stop HAART today? Changed Stopped

19a2. Specify why HAART was changed or stopped *(Tick all that apply)*

- Toxicity / Side effects
- Clinical treatment failure
- Pregnancy
- Immunologic treatment failure
- Risk of pregnancy
- Virologic treatment failure
- Newly diagnosed TB
- Poor adherence
- New drug available
- Illness, hospitalization
- Drug not available
- Other (specify)
- Patient lacks finances

(Skip to 20)

19b. If no, is patient ELIGIBLE for therapy? Yes No Not yet determined *(If Eligible go to 19b1; if NOT eligible or NYD go to 22)*

19b1. If ELIGIBLE for therapy then by what criteria *(tick all that apply)*?

- CD4 count CD4 % Date (DD/MM/YYYY) / /
- WHO Clinical Stage 1 2 3 4 Viral Load
- Patient on HAART/ARV in past

19c. Did you initiate HAART/ARV treatment at this clinic visit, excluding PMTCT and PEP? Yes No *(If YES go to 19c1 If No go to 19c2)*

19c1. If yes, what was the WHO stage 1 2 3 4

19c2. If NO, specify:

- Patient has not completed HAART protocol
- Patient preference
- Patient currently on drugs which may interact with HAART/ARV
- Patient too ill to begin HAART today
- Other (specify)

20. Has the patient completed HAART protocol? Yes No

21. What ARV medications were prescribed or continued today

- AZT-3TC-EFV
- TDF-ABC -LPV/rit
- AZT-3TC-NVP
- TDF 3TC EFV
- AZT-3TC- LPV/rit
- TDF 3TC NVP
- d4T(30mg)-3TC-EFV
- None
- d4T(30mg)-DDI-LPV/rit
- Other (specify)
- d4T(30mg)-3TC-NVP

22. Did you initiate or continue Cotrimoxazole today? Yes No *(If YES go to 23, If NO go to 22a)*

22a. If no, why?

- Side effects/ toxicity Patient preference
 Stockout/drug supply interruption Other (Specify)

23. Did you initiate or continue any of the following medications today (tick all that apply)?

- Dapsone Fluconazole Multivitamin supplement None of the above

24. Other medications prescribed during this visit

Medication	Dose (mg)	Frequency (per day)	Start date	
1.				
2.				
3.				
4.				

25. What laboratory tests were ordered today (tick all that apply)

- ALT Hgb Viral Load
 cd4 HIV ELISA Confirmatory test Widal Test
 Chest X-ray LFT None
 Creatinine Lactic Test Other (specify)
 Complete Blood Count Urinalysis

Comments

For the data use only (tick after scanning the form)

Scanned Date ___/___/_____ Name of data person

HOPE CLINIC ADULT MEDICAL SCREENING

HOPE ID Number

Site Code Today's date (DD.MM.YYYY) Interviewer number

 /

 /

HISTORY OF PRESENT ILLNESS

PAST MEDICAL HISTORY

1. Has the patient ever had pulmonary TB in the past?

Yes No Unknown *(If YES go to 1a, If NO or unknown go to 2)?*

1a. If YES, what was the diagnosis based on *(tick all that apply)*

- Chest X-ray
- Sypmtoms (persistent cough >2 weeks, fever, night sweats, etc)
- Failure to respond to empirical antibiotics
- Sputum
- Other (specify)
- Unknown

1b. Was the patient treated

Yes No Unknown *(If YES go to 1c, If NO or unknown go to 2)*

1c. If YES, specify treatment

- EH SHRZE
- RHZ unknown
- RHZE Other (specify)
- RH

S=streptomycine
H=Isoniazid
R=Rifampicin
Z=Pyrazinamid
E=Ethambutol

1d. If YES, did the patient (tick one)?

- Never completed full treatment
- Doesn't know if received full treatment
- Completed Full Treatment

Date started (DD/MM/YYYY) / /

Date stopped (DD/MM/YYYY) / /

2. Does the patient currently have Extra pulmonary TB? Yes No

3. Does the Patient have Pulmonary TB? Yes No *(If YES go to 3a, If NO go to 4)*

3a. If YES, what was the diagnosis based on (tick all that apply)

- Chest X-ray
- Symptoms (persistent cough >2 weeks, fever, night sweats, etc)
- Failure to respond to empirical antibiotics
- Sputum
- Other (specify)
- Unknown

4. Is the patient currently on treatment for TB (either PTB or EPTB) *(If YES go to 4a If NO or Unknown go to 5)*

Yes No Unknown

4a. If yes, specify treatment start date (DD.MM.YYYY) / /

4b. If YES, specify treatment

- EH SHRZE
- RHZ unknown
- RHZE Other (specify)
- RH

S=streptomycine
H=Isoniazid
R=Rifampicin
Z=Pyrazinamid
E=Ethambutol

4c. Is the patient currently being treated for TB at coptic? Yes No *(If YES go to 5, If NO go to 4d)*

4d. If NO, specify where:

- Private hospital
- Public hospital
- Other government facility
- Other (specify)

5. In the past month, has the patient experienced any of the following? (tick all that apply)

- Dyspareunia Vaginal itching/burning
- Genital sores or ulcers Vaginal discharge
- Lower Abdominal pain Urethral discharge
- Painful micturation(Dysuria) None
- Testicular pain or swelling

6. Has the patient ever had or been told he/she had a sexually transmitted infection? Yes No Unknown

6a. If yes, specify (tick all that apply)

- Chlamydia Trichomonas vaginalis
- Chancroid Syphilis
- Herpes Unknown
- Neisseria gonorrhoea Other specify

7. Does the patient currently have, or has the patient ever had, any of the following conditions (tick all that apply)

WHO stage 1	
Asymptomatic HIV infection	
Persistent generalized lymphadenopathy (PGL)	
WHO stage 2	
Herpes Zoster (within last 5 years)	
Minor Mucocutaneous Manifestations	
Recurrent Upper Respiratory Infections	
Weight loss < 10% of Body weight	
WHO stage 3	
Severe Bacterial infections (i.e Pneumonia, pyomyositis)	
Oral Candidiasis (Thrush)	
Unexplained chronic diarrhea (> 1 month)	
Unexplained Prolonged Fever (intermittent or constant, > 1 month)	
Oral Hairy Leukoplakia	
Tuberculosis, Pulmonary (within last 12 months from today)	
Weight loss > 10% of body weight	
WHO stage 4	
Candidiasis (Esophageal, Bronchi, Trachea, or lungs)	
Cryptococcosis, Extrapulmonary	
Cryptosporidiosis with Diarrhea (> 1 month duration)	
Herpes Simplex (mucocutaneous > 1 months, or visceral or any duration)	
HIV Encephalopathy	
HIV Wasting Syndrom	
Kaposi's Sarcoma (KS)	
Lymphoma	
Atypical Mycobacteriosis, Disseminated	
Tuberculosis, Extrapulmonary	
Progressive Multifocal Leukoencephalopathy (PML)	
Mycosis, disseminated endemic (i.e., histoplasmosis, coccidiomycosis)	
Pneumocystis Carinii Pneumonia (PCP)	
Salmonella Septicemia, Non-typhoid	
Toxoplasmosis, CNS	

8. What is the WHO Clinical Stage of the patient? (tick one) 1 2 3 4

9. Last CD4 count Unknown Not tested
- 9a. Last CD4 count date (DD.MM.YYYY) / / Unknown
- 9b. Last Viral load undetectable Unknown Not tested
- 9c. Last viral load date (DD.MM.YYYY) / / Unknown

MEDICATIONS

10. Has the patient ever taken or is the patient presently on HAART excluding for the purpose of PMTCT and PEP?

- Yes No *(If YES go to 10a, if NO go to 11)*

10a. If YES, specify history below

	Medication (tick all that apply)										
	d4T	3TC	AZT	DDI	ABC	NVP	EFV	LPV/rit	TDF	Truvada	Other (Specify)
First regimen											
Second regimen											
Third regimen											

	Generic or brand (tick one)	CD4 count at time of regimen initiation (if known)	Adherence (1=V. poor, 2=poor, 3=Fair, 4= Good, 5=Excellent)	Date started (DD/MM/YYYY)	Did patient stop?	If yes, Date stopped (DD/MM/YYYY)
First regimen	 Generic  Brand  Unknown	       Unknown		 /  /      	 Yes  No	 /  /      
Second regimen	 Generic  Brand  Unknown	       Unknown		 /  /      	 Yes  No	 /  /      
Third regimen	 Generic  Brand  Unknown	       Unknown		 /  /      	 Yes  No	 /  /      

If stopped why? (tick all that apply)

	Costs	Side effects	Failure of therapy	New diagnosis TB	Drug out of stock	Doctor orders	Unknown	Other (Specify)
First regimen								
Second regimen								
Third regimen								

11. Is patient taking any of the following medications? (tick all that apply)

- Antimalarial medications
 Dapsone
 Herbal traditional medications
 None of the above
 Cotrimoxazole
 Fluconazole
 Multivitamin supplements

12. What other medications is patient currently taking?

Medication	Dose (mg)	Frequency (per day)	Start date	Stop date
1.				
2.				
3.				

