9. Will any of the subjects or their third-party payers be charged for any study procedures?

No Yes If yes, explain:

10. Where will the study procedures be carried out?

The study will be carried out in Nairobi, Kenya at the Coptic Hospital. IRB approval for this PHE has been granted by Kenyatta National Hospital (KNH) in Kenya and the University of Washington (UW).

D. RISKS AND BENEFITS

1. Describe nature and degree of risk of possible injury, stress, discomfort, invasionofprivacy, and other sideeffects from all study procedures, drugs and devices (standard and experimental), interviews and questionnaires. Include psycho-social risks as well as physiological risks. Include risks of withholding standard care or procedures if this is the case. Do not reference the consent form.

The study may collect personal information that may be embarrassing for the subject to talk about. As part of the study, the subject may meet other patients from this clinic whom she may know from outside the clinic. We will be collecting blood samples using a needle and syringe. The puncture of the needle may be uncomfortable and leave a bruise and may cause infection or fainting. Collection of biopsy samples through the pelvic exam may cause: mild discomfort as the subject is examined, small amount of bleeding from the vagina for 1-2 days, and mild to moderate cramping for 5 minutes that is similar to mild menstrual pain. If the subject undergoes cryotherapy or LEEP, then she may experience mild abdominal cramps for less than 10 minutes, discharge from the vagina for about 2 weeks, and/or bleeding for several days. Possible serious complications

include excessive bleeding or infection. Additionally, some studies have shown that cervical treatment is associated with pregnancy complications including premature rupture of membranes, premature contractions, infections and cervical incompetence.

If the subject undergoes a biopsy, she is requested not have sex for 10 days. The reason is that if her partner is not infected with HIV, then he may be at greater risk of becoming infected with HIV after the biopsy procedure because of a possibility of increased HIV shedding from the cervix. The participant may also be at increased risk of infection at the site of the biopsy. If the subject has received cryotherapy or LEEP, then, for the same reasons as the biopsy, we suggest that she not have sex for 4 weeks after it is performed.

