Notebooks, folders and CDs will move between the study clinic site and the KNH data office in a direct manner to minimize handling of data. Information will be transported by private vehicle used by the study. There will be two CDs to back up study data, one to be kept with the administrator at an off-site location and one with the senior data analysis in a locked closet at KNH. Data files on the computer and CDs will be password protected, accessible only by data staff. Additionally, patient identifying data will be kept in a separate, locked folder from the clinical data to maximize confidentiality when reading clinical materials. All data, including physical medical files, will be physically locked when not in transport - both at the study site and at the office at KNH - to assure that only

designated staff will have access to the files. The study coordinator will be responsible for ensuring patient confidentiality for both electronic data and the medical files.

4. Will you place a copy of the consent form or other study information in the subject's medical or other personal record?

No Yes. If yes, explain why this is necessary.

5. Do you anticipate using any data (information, specimens, etc.) from this study for other studies in the future?

No Yes If "Yes," explain and include this information in the consent form.

Specimens may be tested for HPV at a later date. Data and specimens are requested to be stored from the participant for 10 years following enrollment for possible use in other HIV and cervical studies in the future. Approval from the UW and KNH IRBs will be obtained before any of these studies are performed.

F. ADDITIONAL INFORMATION

1. If the study will involve radiation exposure to subjects, e.g., X-rays, radioisotopes:

Pending Approved NA

2. Will you need access to subjects' medical, academic, or other personal records for screening purposes or during this study?

No Yes. If yes, specify types of records, what information you will take from the records and how you will use them.

Subjects will be enrolled at the Hope Center for their HIV care and their medical records contain information on what type of treatment they have received and the severity of their condition. We will access these records to determine what type of antiretroviral treatment they've been exposed to and their clinical status according to medical examination and laboratory values including CD4 count. This information is included in the consent form.

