Outcome of Adverse Event:

All AEs must have their outcome assessed as either “resolved without sequelae”, “resolved with sequelae”, “ongoing”, “death”, “unknown.” The study clinician is responsible for assessing outcomes and recording them on the appropriate CRF.

Definition of Serious Adverse Event (SAE)

An SAE is defined as an AE that meets one of the following conditions:

- Death during the period of protocol defined surveillance
- Life-threatening event (defined as a subject at immediate risk of death at the time of the event)
- An event requiring inpatient hospitalization or prolongation of existing hospitalization during the period of protocol defined surveillance
- Results in congenital anomaly or birth defect
- Results in a persistent or significant disability/incapacity
- Any other important medical event that may not result in death, be life threatening, or require hospitalization, may be considered a serious adverse experience when, based

upon appropriate medical judgment, the event may jeopardize the subject and may require medical or surgical intervention to prevent one of the outcomes listed above.

Data Safety and Monitoring Plan

Introduction

The data safety and monitoring board (DSMB) will act in advisory capacity to the CDC, UW, KNH, UoN, Coptic Hospital, and IARC – WHO to monitor patient safety and evaluate treatment interventions for this study. [name] (UW) will be Chairman of the DSMB.

After its first meeting around study initiation, the DSMB will be responsible for reviewing interim safety and efficacy analyses at five time points during the 3 year study period. These meetings and reviews of interim analyses are expected to occur at approximately 4, 9, 15, 21, and 27 months after study initiation.

- 1) The first meeting will take place when 100 participants have received the study intervention, and this is expected to occur around 4 months after study initiation.
- 2) The second meeting will take place when 75 participants have received Month 6 Pap smear results, and this is expected to occur around 9 months after study initiation.
- 3) Thereafter, DSMB meetings and interim analyses will occur every 6 months after this second meeting or approximately at 15, 21, and 27 months after study initiation.

The DSMB will have the following responsibilities:

1. Review the research protocol and plans for data safety and monitoring;

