The meetings will mainly be open sessions. These sessions will be attended by the Principal Investigators or designee. Other research staff may attend the open sessions but this is up to the discretion of the PI. Issues discussed at open sessions will include conduct and

progress of the study, including patient accrual, compliance with protocol, and problems encountered. Patient-specific data and treatment group data will not be presented in these sessions.

Closed sessions may be requested by the DSMB at any time and will be attended by voting DSMB members and the unblinded statistician. Any other trial staff may be requested to attend by the DSMB. All safety and efficacy data will be presented at this session. The discussion at the closed session is completely confidential.

Should the DSMB decide to issue a termination recommendation, the full vote of the DSMB will be required. In the event of a split vote, majority vote will rule and a minority report will be appended. An appeal may be filed by study PIs if a termination decision is made.

Study Stopping Criteria

The DSMB may recommend stopping the study for the following reasons:

- The data show a significantly increased risk of serious adverse effects in one of the treatment arms.
- Interim efficacy analyses show significant treatment benefits or futility in the one treatment group. The interim efficacy analyses are based on pre-specified stopping boundaries for the primary endpoint of the study which preserve the study wide Type I error rate.
- It becomes clear that successful completion of the study is not feasible (e.g. there is an excess of patient dropout, missing data, lack of recruitment etc).

Interim Efficacy Analyses

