If yes, indicate:

c. Duration ___ ___ days

d. Color

 Yellow Brown White Clear

Other, specify

e. Smell

Malodorous

No odor

Other, specify

f. Volume

Stain pants

Requires sanitary pad

Other, specify

4. Has the patient experienced any fever after the last visit?

Yes No

If yes, specify duration ___ days

5. Did the patient seek medical care for these or other complaints?

Yes No

If yes, specify what complaint prompted the participant to seek care:

Abdominal pain

Fever

Vaginal Bleeding

Vaginal discharge

a. Other, specify

If yes, specify where the participant sought care:

Study clinic

Hope Center

Coptic Hospital

KNH

b. Other, specify

6. Was the participant's condition possibly due to a study procedure? (Ask if any of questions 1-4 is yes)

Yes No

If any question 1-4 is Yes and the condition is not expected as per study protocol, or is more severe than expected, fill an AE form.

7. Date of last menstrual cycle (dd/mm/yyyy)

8. Have you ever had vaginal sex since treatment? Yes No Refused

Other (specify) _____

8 (a). If yes, how many times? ___

8(b) If you have had vaginal sex since treatment, how often did you use condoms during sex?

Always (100%) Most of the time (75-99%)
 Half of the time (50%-74%) Sometimes (25-49%)
 Rarely (1-25%) Never (0%)
 Refused Don't know Other, specify _____

9. Do you think you may be currently pregnant? Yes No

10. Are you currently on antiretroviral medications?

Yes Refused Other, specify

No Don't know

If No, Refused, or Don't Know, skip to Q14

If yes, specify current medications and original start date.

- d4t, 3tc, nvp
- d4t, 3tc, efv
- azt, 3tc, nvp
- azt, 3tc, efv
- Other specify

Original ARV start date (dd/mm/yyyy)

11. During the last 7 days, how many antiretroviral pills did the patient MISS taking?

12. During the last 30 days, how many antiretroviral pills did the patient MISS taking?

(If Q11 and Q12 patient did not MISS taking any pills skip to Q14)

13. If the patient missed any doses, please specify reasons (check all that apply)

- Toxicity/ side effect
- Share with others
- Forgot
 - c. Felt better
- Too ill
- Stigma, disclosure or privacy issues
- Drug out of stock
- Patient lost or ran out of pills
- Delivery /travel problem
- Inability to pay
- Alcohol
- Depression
 - d. Other specify

B: DIAGNOSIS

14. Is there any new infection that was related to the procedure since the last visit?

Yes No

If yes, specify and fill an Adverse Event questionnaire:

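### Obstetric harm is named as a treatment risk, but no study form shown asks routinely about pregnancy after week 3 or records a pregnancy outcome

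*Combined protocol and SAP*

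**What the plan says.** **Risk and stakes.** Ethics, section D item 1, states that "some studies have shown that cervical treatment is associated with pregnancy complications including premature rupture of membranes, premature contractions, infections and cervical incompetence". The Background discusses two studies of women treated with LEEP (one also covering laser methods). Neither found more preterm delivery, but one found more premature rupture of membranes and the other more pregnancy complications. The SAE definition includes an event that "Results in congenital anomaly or birth defect". Under Study Stopping Criteria, the DSMB may recommend stopping if "The data show a significantly increased risk of serious adverse effects in one of the treatment arms".

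**Study forms.** The Shedding form, used at weeks 1, 2 and 3 after treatment, asks "Do you think you may be currently pregnant". Study Procedures item 5 lists what is done at months 6, 12, 18 and 24: a Pap smear with HPV testing, blood for CD4 count and the Pap Smear questionnaire. It lists no pregnancy question or test. The Pap Smear, Follow-up and Exit forms have no pregnancy or delivery item. The Colposcopy form, which can be ticked for months 6 to 24, has a pregnancy-test result field, and Study Procedures item 2 requires a test before any cervical procedure.

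**Hope Clinic records.** The Adult Medical Follow-up form records current pregnancy (item 15), asks "Has the patient delivered in the past 18 Months" (item 17) and carries the instruction "If yes, complete pregnancy Close -Out form". It also records the child's age or that the child is not alive (item 17b). Study Population & Recruitment opens all Hope information to the study after consent. Ethics, section F item 2, gives the purpose: "We will access these records to determine what type of antiretroviral treatment they've been exposed to", together with clinical status and laboratory values. Pregnancy is not named there.

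**The concern.** The two arms are different procedures on the cervix, and the obstetric evidence that the Background cites includes LEEP but not cryotherapy, so this harm could plausibly differ by arm. The trial is meant to inform PEPFAR policy on which procedure to use, and its safety evidence is the by-arm adverse event data reviewed by the DSMB.

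If pregnancies are not identified and followed to an outcome in the same way for everyone, a report of no excess serious events in either arm says little about obstetric harm. A low count could mean few events or few questions, and without the number of pregnancies per arm there is no denominator to tell these apart.

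**Working it through.** The plan gives no pregnancy figure to reproduce. The check is a form-by-form comparison, followed by an illustration of scale.

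**1. What each source can record after treatment**

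| Source | When | What it can show |
|---|---|---|
| Shedding form, item 9 | weeks 1–3, all randomised women | whether she thinks she is pregnant |
| Pap Smear form | months 6–24 | no pregnancy item; uterine size if palpated |
| Follow-up form, item 1 | months 6–24 | consultations; reasons are check-up, sickness or other |
| Colposcopy form, item 4 | months 6–24, only if cytology indicates biopsy | current pregnancy-test result |
| Adverse event inquiry and form | every visit | free text, no obstetric prompt |
| Exit form | exit | no pregnancy or outcome item |

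**2. Coverage of the routine question.** 3 of about 104 post-treatment weeks: 3/104 = 2.9%. A pregnancy conceived after treatment cannot reach delivery by week 3, so this question can capture no delivery outcome.

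**3. The colposcopy route.** It records status, not outcome. If the test is positive, the form directs staff to the Exit form, which has no outcome field. It may also be uneven by arm: at the design rates of 14% and 4% recurrence, 200 × 0.14 = 28 women on cryotherapy and 200 × 0.04 = 8 on LEEP would have a recurrence, so more cryotherapy women would be tested. In addition, the form skips item 4 when colposcopy was done before, which does not fit the requirement of a test before any cervical procedure. Those two passages must be reconciled.

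**4. Illustrative scale.** From the plan: 200 women per arm, 2 years, up to 20% lost. Assumed, because the documents do not say: 5 to 15 pregnancies per 100 woman-years and a 10% complication rate.

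- Woman-years per arm: 200 × 2 = 400 with no loss; 400 × 0.8 = 320 if 20% of the time is lost.
- Pregnancies per arm: 0.05 × 320 = 16 to 0.15 × 400 = 60. At 2 per 100 the low end would be 0.02 × 320 = 6.4.
- Term deliveries within follow-up: with conceptions spread evenly over 24 months, those in the last 9 deliver after exit. The share delivering earlier is (24 − 9)/24 = 0.625, giving 16 × 0.625 = 10 to 60 × 0.625 = 37.5, about 38.
- Half-width of a 95% interval for the arm difference, 1.96 × √(2 × 0.1 × 0.9 / n): n = 10 gives 0.263; n = 37.5 gives 0.136. That is about ±26 to ±14 percentage points.
- Expected events per arm: 0.1 × 10 = 1 to 0.1 × 37.5 ≈ 4. With so few, the normal approximation is rough and serves only to show scale.

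**5. Access to Hope data.** Data Management (Introduction) says study data will not be linked to the Hope dataset. The Data Manager's duties include coordinating transfer of Hope data to the research databases. Study Population & Recruitment opens all Hope information after consent, and Statistical Methods already plans to read clinical files for antiretroviral data. These statements do not agree.

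**The case against.** The best defence is that later collection is prompted. Staff must ask every woman about new medical problems since her last visit, the Follow-up form asks about consultations and has room for six, the adverse event form has boxes for months 6 to 24, and any hospitalisation is an SAE. Pregnancy outcome is not a study objective, and the Background presents obstetric risk as a controversy. Counts would be too small to drive a stopping decision.

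Much of this stands, and it rules out several stronger readings that a reader might infer:

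- *That pregnancy is recorded only up to week 3.* The Colposcopy form can hold a test result at months 6 to 24.
- *That later events appear only if a woman volunteers them.* The adverse event inquiry and the consultation item are prompts, though neither mentions pregnancy.
- *That most obstetric events would be missed.* Nothing in the documents gives the capture rate of the open inquiry.
- *That this is the only lasting harm named.* The section on reporting adverse events also lists severe cervical stenosis.
- *That the Hope pregnancy fields are definitely left unused.* Clinical status could be read to include them; the text is unclear.
- *That Hope records would supply every named outcome.* The items shown give pregnancy, delivery, child's age and child not alive. The Pregnancy Monitoring and Close-Out forms are not in the text available. Nor are the consent pages or the study-tests flow diagram, so a follow-up test or a reporting instruction there cannot be excluded.

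None of this supplies a routine question after week 3, a denominator of pregnancies by arm or an outcome field.

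**Conclusion.** The concern holds as a gap in systematic safety capture. On the forms shown, routine questioning about pregnancy stops at week 3 and no form has a pregnancy-outcome item, although the protocol names obstetric complications as a treatment risk and birth defects as serious events. Later detection depends on a test tied to cervical procedures or on general inquiries.

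The size is uncertain. Under the assumed incidence, about 16 to 60 pregnancies per arm would not be followed systematically, with roughly 10 to 38 term deliveries inside follow-up. An interval of about ±26 to ±14 points at an assumed 10% complication rate means that the data could describe obstetric safety but not test it. The primary comparison of recurrence is unaffected. The change is worth making because it is cheap and because a statement of no excess serious harm would otherwise be hard to interpret for pregnancy.

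**What to change.** 1. For each randomised woman, abstract items 15, 17 and 17b of the Hope follow-up form, plus the Pregnancy Monitoring and Close-Out forms as far as they hold outcomes, before each DSMB report and at the end of follow-up. Item 17 looks back 18 months, so use the child's age to check that the delivery followed treatment.
2. Enter obstetric complications, fetal or neonatal death and birth defects on the study adverse event form.
3. Tabulate pregnancies and these events by randomised arm as descriptive safety data, without a formal test.
4. Reconcile the no-linkage sentence in Data Management with the Data Manager's duties, the consent-based access in Study Population & Recruitment and the purposes in Ethics, section F item 2, so that this abstraction is clearly allowed.
5. If the Hope pregnancy forms prove not to hold the named complications, add a pregnancy and outcome item to the existing Follow-up form.

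The cost is some chart abstraction, one safety table and a few reconciled sentences; steps 1 to 4 need no new visits, tests or participants. The limits are few events, no coverage of women who leave the Hope Center, no capture of deliveries after exit, and uncertainty over whether Hope records hold membrane rupture, preterm birth or birth defects.
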